#### **6.5.5. PK and Pill Compliant Per-Protocol (PK/PC-PP) Population**

The PK Compliant Per-Protocol Population will include subjects who:

1. Met all inclusion/exclusion criteria.
2. Did not receive concomitant medications that are prohibited due to their potential impact on HCV viral load or the pharmacokinetic concentration of either agent (BEM or RZR).
3. Have a collected or imputed (per Table 5) posttreatment viral load assessment at post treatment week 12 (week 4 for lead-in subjects), unless the subject discontinues early for virologic failure or AE, in which case the ET visit assessment may be used.
4. Completed treatment, discontinued treatment early due to virological failure, or discontinued treatment early due to drug-related AE.
  - Completed treatment is defined as being in  $\geq 90\%$  compliance with the study drug regimen. Compliance will be calculated using drug compliance data collected on the eCRF.

and

- Adequate exposure corroborated by a Pharmacokinetic Review Committee that is blinded to all other study data. The PK Review Committee will utilize trough PK measurements collected during the dosing period of the study.

All efficacy analyses will be performed on this population.

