### **5.8.2. Concomitant Medication**

Concomitant therapy consists of any medication (eg, prescription drugs, over the counter drugs, vaccines, herbal or homeopathic remedies, nutritional supplements) used by a subject in addition to study drug treatment. All such medications should be reported to the investigator and recorded on the Concomitant Medications electronic Case Report Form (eCRF). Concomitant medications should be used according to their label.

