### **5.8.5. Prohibited Therapy**

Concomitant use of the following is prohibited:

- Investigational drugs (other than protocol-mandated study treatment)
- HCV treatments (other than protocol-mandated study treatment)
- Hydroxychloroquine or amiodarone

- Strong and moderate inducers of cytochrome P450 3A and/or P-gp including anti-infectives (nafcillin, rifampin), anticonvulsants (carbamazepine, phenytoin, phenobarbital), endothelin antagonists (bosentan), and wakefulness-promoting agents (modafinil). For a comprehensive list of cytochrome P450 3A inducers, refer to: <https://go.drugbank.com/categories/DBCAT000492>; for a comprehensive list of P-gp inducers, refer to: <https://go.drugbank.com/categories/DBCAT002666>

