### **6.8.2. Missing Start and Stop Dates for Prior and Concomitant Medication**

Where the start date for a concomitant medication is missing, the medication will be assumed to have started prior to enrolment in the study. Where the stop date for a concomitant medication is missing, the medication will be assumed to be ongoing to the date of the subject's last assessment.

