### **8.7.3. Subjects Receiving Rescue Medications for HCV**

Subjects that relapse or fail to achieve SVR and begin non-IP HCV treatment will have failure imputed to timepoints that are subsequent to beginning their non-IP HCV treatment regimen regardless of the observed result HCV viral load results. Imputed timepoints should be excluded from quantitative viral load analyses.

The list of rescue medications is presented in Appendix 2.

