#### 8.7.4. Primary Efficacy Analysis

The primary efficacy endpoint is the proportion of subjects in the PK and Pill compliant per-protocol population (PK/PC-PP) achieving sustained virologic response at 12 weeks post-treatment (SVR12). Table 5 will be used to derive SVR12 in the analysis populations.

**Table 5. Determination of primary outcome (SVR12) for subjects who meet all I/E criteria, did not receive prohibited medications and otherwise met population definition criteria.**

On-Treatment Experience	Has	Has	EOT or	Qualifying Result	Primary Outcome
	12W Post RNA	24W Post RNA	W4 Post HCV Positive		
Met Population Specific Criteria	Y			12W Post	12W Post Result
	N	Y		24W Post	24W Post Result
	N	N	Y	Last value	Failure
	N	N	N	NONE	Excluded from population
Early DC for Drug-Related AE	Y				12W Post Result
	N	Y			24W Post Result
	N	N	Y		Failure
	N	N	N		Failure
Early DC for Virologic Failure			Y		Failure
Other					Excluded from population

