## **9. SAFETY AND TOLERABILITY**

### **9.1. Overall Summary of Tolerability**

All adverse events will be coded according to the Medical Dictionary for Regulatory Activities (MedDRA) and will be summarized for the safety population. Only treatment-emergent adverse events (TEAE) will be summarized. Treatment emergent adverse events are those with start date/time within the treatment period, defined as the time from first study drug administration to 4 weeks post treatment. Events that occur after 4 weeks with relationship to study drug recorded as 'related' will also be considered as treatment emergent. If the AE onset date is missing or partial, the conventions described in Section **Error! Reference source not found.** will be used to determine if the event is treatment emergent.

Adverse event severity will be graded according to the Division of AIDS (DAIDS) Table for Grading the Severity of Adult and Pediatric Adverse Events, Version 2.1 dated July 2017.

An overall summary of adverse events will be presented and include tabulations (number and %, unless otherwise indicated) for the following:

- Subjects with at least one TEAE, overall and by worst grade
- Total number (number only) of TEAEs
- Deaths
- Subjects who discontinued study due to an AE
- Subjects who discontinued treatment due to an AE
- Subjects with a treatment related AE resulting in treatment discontinuation
- Subjects with a serious adverse event (SAE)
- Subjects with a treatment related SAE
- Subjects with a treatment related AE, overall and by worst grade
- All Adverse Events will be listed

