## **9.4. Concomitant and Other Medications**

Concomitant medications (CM) are medications that are administered during the treatment-emergent period. If the (CM) onset date and/or end date is missing or partial, the conventions described in Section 6.8.2 will be used to determine if the medication is concomitant. Medications will be presented based on WHODRUG coding.

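### Read literally, per-protocol criterion 2 removes a virologic failure who starts other HCV treatment within 4 weeks of the last dose, although SAP 8.7.3 and Table 5 score that subject as a failure

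*SAP*

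**What the plan says.** **Population rule.** Criterion 2 of EE-PP, PC-PP and PK/PC-PP (SAP 6.5.3 to 6.5.5; matching text in protocol 8.1.3 and 8.1.4) requires that the subject "Did not receive concomitant medications that are prohibited due to their potential impact on HCV viral load" or on the concentration of either drug. The prohibited list in protocol 5.8.5 includes "HCV treatments (other than protocol-mandated study treatment". Criterion 2 has no time limit of its own and no exception for treatment begun after failure.

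**Meaning of concomitant.** Protocol 5.8.2 describes it as medication "used by a subject in addition to study drug treatment". SAP 9.4 is wider: "Concomitant medications (CM) are medications that are administered during the treatment-emergent period". SAP 9.1 gives the length of that period: it is "defined as the time from first study drug administration to 4 weeks post treatment".

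**Outcome rule.** SAP 8.7.3 says that subjects who relapse or do not reach SVR, and then begin non-study HCV treatment, "will have failure imputed to timepoints that are subsequent to beginning their non-IP HCV treatment regimen". In Table 5 (SAP 8.7.4), early discontinuation for virologic failure is scored as failure. But the title restricts the table to outcomes "for subjects who meet all I/E criteria, did not receive prohibited medications and otherwise met population definition criteria", and here the word concomitant is missing.

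**The concern.** The population rule and the outcome rule give different answers for the same subject. The population criteria must all be met, so criterion 4, which admits subjects who stop early for virologic failure, cannot bring back a subject whom criterion 2 has removed. Nothing states that 8.7.3 takes precedence.

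The consequence runs one way. Treatment begun because study treatment failed is given only to failures, so excluding those subjects takes failures out of both numerator and denominator of the failure rate and leaves the responders untouched. The estimates at stake are SVR12 in PK/PC-PP (primary), SVR12 in EE-PP and PC-PP, and virologic failure and SVR24 in all three sets (SAP 8.8). The trial is open-label, so an ambiguity left in the text would be settled by people who can see the outcomes.

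**Working it through.** **1. Who is affected.** Setting the passages side by side:

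| Subject | Criterion 2 with SAP 9.4/9.1 | SAP 8.7.3 and Table 5 rows |
|---|---|---|
| On-treatment failure, other HCV treatment begun within 4 weeks of last dose (e.g. 2 weeks after stopping) | Prohibited and concomitant: excluded | Failure |
| Failure, other HCV treatment begun more than 4 weeks after last dose | Not concomitant: kept | Failure, though the Table 5 title, read literally, could still shut the subject out |
| Relapse first seen at the follow-up Week 4 visit | Visit window is ±5 days, so at most about 5 days of the 28 remain: usually kept | Failure |

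The direct conflict is the first row. The second row is a conflict only through the Table 5 title.

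**2. The plan's own figures reproduce.** Inputs: 280 enrolled, 75 with GT3, 95% evaluable (SAP 4.1 and 4.3.1). 280 × 0.95 = 266, and 75 × 0.95 = 71.25, taken as 71. The bounds in SAP Table 3 match the one-sided 95% Wilson lower limit with z = 1.645:

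L = [p + z²/(2n) − z·√(p(1−p)/n + z²/(4n²))] / (1 + z²/n)

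For example, 255/266 = 95.9% gives 93.35% (table: 96% gives 93%), and 68/71 = 95.8% gives 89.9% (table: 96% gives 90%).

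**3. Effect of dropping k failures.** Assumption: 13 failures in 266, all virologic. The documents give neither the failure count nor k. For k = 0: p = 253/266 = 0.9511, z²/(2n) = 0.00509, root term = 0.01358, so L = (0.9511 + 0.0051 − 0.0223)/1.0102 = 92.4%. The other rows use the same formula with 253/(266 − k).

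| k dropped | SVR12 | One-sided lower bound | Two-sided 95% CI | Virologic failure |
|---|---|---|---|---|
| 0 | 253/266 = 95.1% | 92.4% | 91.8 to 97.1 | 13/266 = 4.9% |
| 1 | 253/265 = 95.5% | 92.9% | 92.3 to 97.4 | 12/265 = 4.5% |
| 2 | 253/264 = 95.8% | 93.3% | 92.7 to 97.7 | 11/264 = 4.2% |
| 4 | 253/262 = 96.6% | 94.2% | 93.6 to 98.2 | 9/262 = 3.4% |
| 6 | 253/260 = 97.3% | 95.1% | 94.6 to 98.7 | 7/260 = 2.7% |
| 13 (arithmetical limit) | 253/253 = 100% | 98.9% | 98.5 to 100 | 0/253 = 0% |

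Each dropped failure adds about 0.36 percentage points near this rate. In GT3, with an assumed 4 failures in 71, dropping one moves 67/71 = 94.4% to 67/70 = 95.7%.

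**The case against.** The strongest reply is that the plan clearly means to keep failures. Criterion 3 makes an exception for early virologic failure, criterion 4 admits it, Table 5 scores it, and 8.7.3 only makes sense if the subjects remain in the analysis. Protocol 5.6.1 describes other HCV treatment as following completion of study procedures, and 5.7 asks early discontinuers to return for follow-up visits, so starts within 4 weeks of the last dose may be rare. The study is descriptive with no hypothesis test, SAP 7.1 tabulates exclusions with reasons, and SAP 8.7.5 repeats all efficacy analyses in the safety population, which has no criterion 2. All of this stands. It limits how many subjects are at risk and makes exclusions visible. It does not settle which rule prevails for an early start, and the safety-population result is supplemental to the primary one.

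Three stronger readings are tempting but not supported:

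- A reader might infer that every failure who receives other HCV treatment leaves the primary population. Under SAP 9.4 and 9.1, treatment begun more than 4 weeks after the last dose is not concomitant, so criterion 2 does not reach it.
- A reader might infer that the lead-in decision would flip. With 60 × 0.95 = 57 evaluable, 7/57 = 12.3% closes enrolment. Dropping one gives 6/56, which meets the limit of 6 in SAP 4.1, but 10.7% still exceeds the 10% rate in SAP 5.1. The two forms of the rule disagree there, so no clear flip follows.
- SAP 6.8.2 says: "Where the start date for a concomitant medication is missing, the medication will be assumed to have started prior to enrolment in the study". A reader might infer that an undated later HCV drug would then look like prior antiviral exposure and breach eligibility. Nothing in the documents lets an imputed medication date overturn an eligibility assessment, and Appendix 2, which lists these drugs, is not available to check.

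**Conclusion.** The conflict is real and confined. For a virologic failure who starts other HCV treatment within 4 weeks of the last dose, criterion 2 excludes and 8.7.3 with Table 5 counts a failure, with no stated precedence. For later starts only the Table 5 title creates doubt. Any resulting bias favours the regimen.

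Its size depends on a count that the documents do not give. It is zero if no failure starts other treatment that early. Under the assumed 13 failures in 266 it is about +0.4 points for one subject, +0.7 for two and +1.5 for four, and two would carry the lower bound past 93%. No stated figure in the plan is wrong on this point. Because the wording decides who belongs to the primary population, it should be settled before database lock.

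**What to change.** These are changes to analysis wording only, with no effect on patient care:

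1. In criterion 2 of SAP 6.5.3 to 6.5.5 and protocol 8.1.3 and 8.1.4, and in the Table 5 title, state that HCV treatment started after the first HCV RNA result meeting a virologic failure criterion does not exclude a subject, that 8.7.3 governs, and that the outcome is failure.
2. Leave criterion 2 otherwise as it is. Narrowing it to the dosing period would keep a subject who stops for a drug-related AE without virologic failure and then starts another HCV regimen. As 8.7.3 covers only those who relapse or do not reach SVR, Table 5 could credit that regimen's cure to BEM + RZR.
3. Extend 8.7.3 so that any subject in an efficacy population who starts non-study HCV treatment before the Week 12 assessment is scored a failure, whatever the later HCV RNA result. This also closes the same gap for starts after the 4-week window and in the safety-population analysis.

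The cost is a SAP revision and a matching protocol clarification, with no new data. The downside is that SVR12 may come out slightly less favourable.

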#### **6.5.6. Pharmacokinetic Populations**

The PK population will include all subjects who received at least one dose of both study drugs taken together and for whom evaluable plasma concentration data are available.

The serial PK-only substudy population will include all subjects who received at least one dose of both study drugs taken together and for whom evaluable drug concentration data are available for the visit when serial blood samples were collected.

The serial PK/VK substudy population will include all subjects who received at least one dose of both study drugs taken together and for whom evaluable drug concentration and VK (HCV RNA) data are available for the visit when serial blood samples were collected.

#### **6.6. Baseline Definition**

Baseline is defined as the last available assessment prior to first dose of study treatment (BEM and/or RZR).

## 6.7. Derived and Transformed Data

### 6.7.1. Baseline Age

Baseline age is the age at the time of enrollment (informed consent date).

### 6.7.2. Study Day

Study day will be calculated from the first dosing date of study drug (FDD) and derived as follows:

- Assessment date  $\geq$  date of first study drug: Assessment Date – FDD + 1
- Assessment date  $<$  date of first study drug: Assessment Date – FDD.

If a subject is enrolled but does not receive any study drug, the enrollment date will be used for reference, in place of FDD.

### 6.7.3. Change from Baseline

Where applicable, change from baseline will be computed simply as the difference between the post-baseline value and the baseline value.

### 6.7.4. Visit Windows

For the purposes of by-visit analyses for scheduled clinical assessments (i.e., excluding patient-reported assessments), visit windows for inclusion in the analysis are defined in Table 4. Note that the definition of baseline is provided in Section 6.

Early termination data will be mapped based on the scheduled Study Day of each scheduled visit as specified in the protocol schedule of events.

Visits assigned as “unscheduled” by labs for safety data and HCV RNA quantitation will be mapped based on the table below. If there is more than one unscheduled visit in a visit window, the visit closest to the target date will be used in by-visit analyses. If there is a tie between the number of days from the target date, the later visit will be used. Unscheduled visits that fall within the protocol-defined visit windows will be summarized in the by-visit analyses only if there is no scheduled visit available in the analysis visit window.

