## LIST OF ABBREVIATIONS

Term	Definition
AE(s)	Adverse event(s)
ALT	Alanine aminotransferase
APRI	Aspartate aminotransferase-to-platelet ratio index
AST	Aspartate aminotransferase
AUC	Area under the plasma concentration-time curve
AUC t	area under the plasma concentration-time curve from time 0 to the last time point (ie, corresponding to a quantifiable concentration)
BEM	Bemnifosbuvir
BMI	Body mass index
CI(s)	Confidence interval(s)
C max	Maximum observed plasma concentration
COVID-19	Coronavirus Disease 2019
CRO	Contract research organization
DAA(s)	Direct acting antiviral(a)
DAIDS	Division of AIDS
DDI	Drug-drug interaction
EC 50/95	50% effective concentration
ECG	Electrocardiogram(s)
eCRF	Electronic case report form
EDC	Electronic Data Capture
E max	Maximal effect
EOS	End of Study, defined as the day in which the subject completes their last assessment; the planned EOS is study Week 32 (i.e., 24 weeks posttreatment)
EOT	End of Treatment, defined as the last day study drug is administered; the planned EOT is at the end of Week 8
ET	Early termination
EU	European Union
FDC	Fixed-dose combination
GCP	Good Clinical Practices
(e)GFR	(Estimated) Glomerular filtration rate
GT	Genotype
HbA 1c	Hemoglobin A 1c
HBsAg	Hepatitis B surface antigen
HBV	Hepatitis B virus
HCC	Hepatocellular carcinoma
HCV	Hepatitis C virus
HIV	Human immunodeficiency virus

ICF	Informed consent form
ICH	International Conference on Harmonisation
IEC	Independent Ethics Committee
IMP	Investigational Medicinal Product
INR	International Normalized Ratio
IRB	Institutional Review Board
LLOQ	(Lower) Limit of quantitation
MDRD	Modification of Diet in Renal Disease
MedDRA	Medical dictionary for regulatory activities
NS	Nonstructural
NS5A	Nonstructural protein 5A
NS5B	Nonstructural protein 5B
PD	Pharmacodynamic
P-gp	P-glycoprotein
PK	Pharmacokinetic(s)
PP	Per protocol
PT	Preferred term / Prothrombin time
QTcF	Fridericia-corrected QT interval
RAV(s)	Resistance-associated variant(s)
RBC	Red blood cell
RZR	Ruzasvir
SAE(s)	Serious adverse event(s)
SAP	Statistical analysis plan
SVR4/12/24	Sustained virologic response at 4/12/24 weeks posttreatment
ULN	Upper limit normal
UPR	uprifosbuvir
VK	Viral kinetics

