### 3. STUDY DESIGN

#### 3.1. General Study Design

This is an open-label trial to evaluate 8 weeks of treatment with BEM + RZR in subjects with chronic HCV infection (Figure 2). Approximately 280 treatment-naïve subjects with genotype (GT) 1, 2, 3, 4, 5, 6, or 7, either without cirrhosis or with compensated cirrhosis, will be enrolled.

A lead-in group of 60 non-cirrhotic subjects will initially be enrolled. At 4 weeks posttreatment, this lead-in group will be evaluated for safety, SVR4, and virologic relapse; enrollment will open to the remaining 220 subjects provided that **CCI** [REDACTED] in the lead-in group experience virologic failure that was not due to poor compliance and no study stopping rules are met (Section 5.6.3).

**Figure 2:** Study Design

a Can be extended to 6 weeks under extenuating circumstances with Sponsor approval.  
BEM = bemnifosbuvir; RZR = ruzasvir; SVR4 = sustained virologic response at 4 weeks posttreatment

Subjects will be screened for up to 4 weeks, although this can be extended for up to 6 weeks for extenuating circumstances with Sponsor approval. Such circumstances may include awaiting reporting of laboratory results or scheduling assessment of cirrhosis (eg, FibroScan®) if needed. Re-screens may be approved on a case-by-case basis by the Sponsor (re-screened subjects will be assigned a new subject number).

At the end of the screening period (Baseline; Day 1), eligible subjects will enter the treatment period and receive BEM + RZR for 8 weeks. After Day 1 during the treatment period, subjects

may self-administer study drugs (ie, IMP) at home, with the exception of subjects who agree to additional PK and/or PK-VK blood sampling as part of up to two substudies. These subjects will be required to take their study drug in the clinic on certain days (see [Table 3](#)).

Subjects will return to the clinic for evaluations at Weeks 1, 2, 4, 6, and 8 (End of Treatment [EOT]) during the treatment period.

Following their last visit of the treatment period (including subjects who prematurely discontinue treatment) subjects will enter the Follow-up period and return to the clinic for evaluations at Follow-up Weeks 4, 12, and 24. End-of-Study (EOS) is defined as the visit at 24 weeks posttreatment.

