a Screening window may be extended to 42 days for extenuating circumstances with Sponsor approval.

b Day 1 assessments performed prior to dosing.

c The last dose is on Day 56. The last visit of the treatment period shall occur no sooner than Day 57 and no later than Day 60 (inclusive).

d Three consecutive determinations collected, with no less than 1 minute between individual ECGs. Complete ECGs prior to any blood draws.

e For females of childbearing potential, serum or urine is acceptable.

f Plasma samples collected for resistance testing. At least one baseline resistance sample is needed (Screening and/or Day 1 predose); there is no protocol deviation if there is one evaluable baseline sample for resistance testing. In addition, the resistance sample is not required for screening and eligibility purposes.

g On Day 1, the PK sample will be obtained predose. The sampling time and time of last dose must be recorded.

h See Table 3

i Subjects may be contacted between visits to assess compliance, concomitant medications, and AEs/SAEs.

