#### **8.7.2.1. On-Treatment Virologic Failure**

On-treatment virologic failure is defined as any of the following, while on-treatment:

- Not achieving  $\text{HCV RNA} < \text{LLOQ}$
- Confirmed 1  $\log_{10}$  increase in HCV RNA from post-baseline nadir (would call this “virologic rebound” if we want to name it in parenthesis)
- Confirmed increase in  $\text{HCV RNA} \geq \text{LLOQ}$  in any subject who achieved  $\text{HCV RNA} < \text{LLOQ}$

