## 8.9. Analysis of Exploratory Efficacy Endpoints

Exploratory efficacy analyses for all populations include:

- Proportion of subjects with SVR12 by HCV genotype and presence of baseline NS5A and NS5B RAVs.
- Proportion of subjects with SVR24 by HCV genotype and presence of baseline NS5A and NS5B RAVs.
- Proportion of subjects with SVR4 by HCV genotype and presence of baseline NS5A and NS5B RAVs.
- The proportion of subjects achieving SVR24, analyzed using the same method as for SVR12.
- Proportion of emergence of NS5A and NS5B RAVs in subjects who experience virologic failure. Results will also be summarized by genotype.
- Proportion of baseline NS5A and NS5B RAVs in subjects who experience virologic failure. Results will also be summarized by genotype.
- Prevalence of specific baseline and treatment-emergent NS5A and NS5B RASs by genotype and by virologic failure at SVR12
- SVR12 will be estimated and presented with 95% CIs by demographics and/or baseline characteristics including prior HCV treatment and baseline viral load (baseline viral load will be categorized using the median as a low-high cut-off point).
- HCV RNA IU/ml log10 value will be tabulated by HCV genotype and the average change from baseline over time will be plotted.
- Qualitative HCV RNA results will be tabulated by HCV genotype over time
- Exposure-response relationships will be explored by scatter plots of drug exposure versus change in HCV RNA IU/ml log10 value.

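### SAP Table 4 counts some visit windows from first dose and others from last dose with no precedence rule, so in early stoppers off-drug HCV RNA samples can be summarised under treatment visits, sometimes under two visits.

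*SAP*

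**What the plan says.** SAP 6.7.4 states that for by-visit analyses of scheduled assessments the "visit windows for inclusion in the analysis are defined in Table 4". Table 4 gives Days 2–11, 12–21, 22–35 and 36–49 for Weeks 1, 2, 4 and 6, with study day counted from first dose (SAP 6.7.2). Week 8 starts at Day 50 and ends at EOT+20. Post Treatment Week 4 is EOT+21 to EOT+69, and Post Treatment Week 12 is EOT+70 to EOT+146.

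The SAP does not define EOT. The protocol's abbreviation list does: "End of Treatment, defined as the last day study drug is administered". For a full course, "The last dose is on Day 56" (Protocol Table 2, footnote c), with the last treatment visit on Days 57 to 60.

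On stopping early, SAP 6.7.4 adds: "Early termination data will be mapped based on the scheduled Study Day of each scheduled visit". Protocol 3.1 and 5.7 send early stoppers into follow-up at Weeks 4, 12 and 24, so they go on giving samples off drug.

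Where a window holds several values, SAP 6.7.5 keeps the one nearest the target day but refers efficacy data to 8.7.1, which keeps the latest HCV RNA value. The only text that ties a visit label to time on drug is the note in 8.7.2.2: Week 8 HCV RNA counts as on-treatment for subjects with 51 or more days of treatment.

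**The concern.** The two sets of windows fit together only if dosing runs close to Day 56. When a subject stops earlier, the EOT-based windows move forward while the Week 1 to 6 windows stay in place. A sample taken weeks after the last dose can then meet the definition of a treatment-period visit, and in the earliest stoppers that of a post-treatment visit as well. SAP 6.7.5 limits each visit to one value per subject; it does not limit a value to one visit.

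What is at stake is the HCV RNA description over time. SAP 8.9 tabulates log10 HCV RNA by genotype, and "the average change from baseline over time will be plotted", for all populations. If virus returns after the drug is stopped, the returning value can enter a Week 4 or Week 6 mean that a reader takes as response during treatment.

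**Working it through.** **Inputs.** Window limits from SAP Table 4; study day from SAP 6.7.2; EOT taken as the actual last dosing day (Protocol, List of Abbreviations); follow-up visits at ±5 days after the last treatment visit (Protocol Table 2).

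**1. The table as planned.** With EOT = Day 56, Week 8 is Days 50–76, Post Treatment Week 4 is Days 77–125 and Post Treatment Week 12 is Days 126–202. Every day from Day 2 carries exactly one label, so the table works for completers.

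**2. Overlap.** Post Treatment Week 4 starts at EOT+21; the Week 6 window ends at Day 49. They overlap when EOT+21 ≤ 49, that is EOT ≤ 28, over 49 − (EOT+21) + 1 = 29 − EOT days. The Week 4 window is also reached when EOT+21 ≤ 35, that is EOT ≤ 14.

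**3. Off-drug days under a treatment-visit label.** These run from EOT+1 to the later of Day 49 and EOT+20.

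| EOT (day) | Off-drug days with a treatment-visit label | Days with two labels |
|---|---|---|
| 8 | 9–49 (41 days) | 29–49 (21 days) |
| 14 | 15–49 (35 days) | 35–49 (15 days) |
| 15 | 16–49 (34 days) | 36–49 (14 days) |
| 28 | 29–49 (21 days) | 49 (1 day) |
| 29 | 30–49 (20 days) | none |
| 56 | 57–76 (20 days) | none |

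These are days, not samples. A day matters only if a sample is taken on it.

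**4. A scheduled sample with two labels.** Last dose Day 15, early-termination visit Day 16. Follow-up Week 4 is Day 16+28±5 = Days 39–49. Every one of those days lies in both Week 6 (36–49) and Post Treatment Week 4 (36–84). Counting from EOT as Table 4 does, the Follow-up Week 4 target EOT+28 has two labels for EOT ≤ 21. A visit five days early has two for EOT ≤ 26.

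**5. An off-drug value displacing an on-drug one.** Week 6 sample on Day 43, dosing stops that day, early-termination visit on Day 48. Both fall in Days 36–49, and Day 48 is nearer to Day 43 (5 days) than to Day 57 (9 days). The nearest-to-target rule of 6.7.5 would keep Day 43; the latest-value rule of 8.7.1 keeps Day 48, which is off drug. For unscheduled samples the route is narrower, because 6.7.4 uses them in by-visit analyses only when the window holds no scheduled visit.

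**6. SVR12.** Post Treatment Week 12 starts at EOT+70, so at Day 71 or later. It clears Day 49 and EOT+20 for every EOT, so there is no overlap.

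**7. Size of one misplaced value (assumption).** The documents give no rebound size. Take 1 log10, the plan's own threshold for a confirmed rise, to 5 log10 as an assumed large rebound, with all targeted subjects contributing a value. At n = 25 (the GT4 target) the shift is 1/25 = 0.04 to 5/25 = 0.20 log10. At n = 75 (GT1a or GT3) it is 1/75 = 0.01 to 5/75 = 0.07. At n = 280 it is at most 5/280 = 0.02.

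**The case against.** **Nominal labels.** Section 6.7.4 says that early-termination and unscheduled data are mapped, which suggests that a scheduled Follow-up Week 4 sample keeps its own label. If so, the double label in step 4 disappears. But the section's opening sentence applies Table 4 to scheduled assessments, and nothing says that nominal labels govern. Early-termination samples are exposed under either reading.

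**Failure classification.** A reader might infer that off-drug rebound would be counted as on-treatment failure. The documents do not support that: "On-treatment virologic failure is defined as any of the following, while on-treatment", so the test is treatment status, not a Table 4 label, and both criteria based on a rise need confirmation. What stands is that the SAP never says how treatment status is judged.

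**Safety data.** A reader might infer that laboratory and vital-sign summaries are broadly contaminated. Protocol Table 2, as far as its extracted form can be read, ends both at early termination. ECGs appear to continue to Follow-up Week 4 but are not scheduled at Week 6. The exposure is mainly early-termination and unscheduled values.

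**Empty Week 8.** With EOT ≤ 29, EOT+20 is below Day 50 and the window has no days. That is not a harm: someone who stopped by Day 29 should have no Week 8 treatment value.

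**Reach.** PC-PP and PK/PC-PP keep early stoppers only for virologic failure or a drug-related AE, and 8.7.3 removes time points after rescue HCV therapy from quantitative viral-load analyses. The study is descriptive throughout. These points stand and limit the consequence.

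**Conclusion.** The gap is real and small. For EOT on or before Day 28, Table 4 gives some days two visit labels (only Day 49 when EOT is Day 28). For any early stopper, it admits off-drug early-termination or unscheduled samples to treatment-visit windows. No other section resolves either.

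The exposed outputs are descriptive by-visit HCV RNA summaries and plots, chiefly in EE-PP, which requires one dose and no completion of treatment, and in the safety population. Early-termination or unscheduled safety values are exposed to a lesser extent. It would be wrong to infer that the primary result is at risk: the Week 12 window never overlaps a treatment window, and the overlap adds a second label without removing the Post Treatment Week 4 one.

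The number affected cannot be computed. The expected 5% outside the per-protocol population (0.05 × 280 = 14) covers all reasons and is not an early-stopping rate. The conclusion assumes that EOT is the actual last dosing day. If it meant the planned Day 56, the overlap would vanish but early stoppers' post-treatment visits would be misdated.

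**What to change.** Define EOT in the SAP as the actual last dosing day, and add to 6.7.4:

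- EOT-based windows take precedence: a sample at EOT+21 or later is assigned only to a post-treatment visit.
- Week 1 to 6 windows end at the earlier of their Table 4 limit and a short stated allowance after last dose. EOT+4 would match the Day 57–60 visit allowance (56+4 = 60). Later samples before EOT+21 are listed but left out of by-visit summaries.
- Week 8 keeps its current limits for subjects with 51 or more days of treatment, consistent with 8.7.2.2, and is not used for others.

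Week 8 needs this separate rule. With last dose on Day 51 or 52, the planned Day 57 sample is at EOT+6 or EOT+5. A uniform EOT+4 limit would drop it although 8.7.2.2 counts it as on-treatment.

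In 8.7.2.1, state that treatment status is judged by dosing dates, and keep the 8.7.2.2 Week 8 note.

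These rules remove every double label, since EOT+4 and EOT+20 both precede EOT+21, and leave a 56-day course unchanged. In step 5, Week 6 would end on Day 47 and the Day 43 value would be kept. The cost is SAP wording, some programming and slightly fewer values at late treatment visits.
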